1.6. JUSTIFICATION OF THE LOW LEVEL OF INTERVENTION

In 2017, the CNEDiMTS (HAS) performed a review of all available publications regarding Urolift device in order to assess its relevance in France in comparison with available standard of care (TURP).

The CNEDiMTS (HAS) performed a comprehensive review of the results of the LIFT study with 3 years follow-up data, of the BPH-6 Study, of an economic evaluation performed by the NICE in the UK, and of all the previously published data. At the end of this process, the experts of the CNEDiMTS (HAS) concluded that Urolift had an entire place in the therapeutic strategy of BOO treatment in France and could be used in daily practice. They assorted this statement by an ASA IV ranking corresponding to a minor improvement compared to standard treatment. They also asked the company (NEOTRACT, INC) to follow-up patients receiving Urolift in France by collecting their clinical characteristics, the number of implants used, the mid-long term functional results, and the need for any kind of retreatment.

Since then, Urolift has been sparsely used in France mainly due to the fact that the price of this single-use device is not covered by the hospitalization and that Urolift is still not reimbursed by the French Healthcare System.

In the setting of the ECOLIFT study, the Urolift device will be used following the exact recommendations of the HAS (same inclusion/exclusion criteria). The ECOLIFT protocol strictly reproduces the clinical use of Urolift without any additional clinical visit or any invasive procedure due to the research protocol as compared to French standard of care (TURP).

Additionally, the aim of our study is not to assess again its clinical effectiveness but to measure its economical value in the setting of the French Healthcare System to support the need of its reimbursement.

Finally, surgeons participating to the ECOLIFT study will have to be experienced with this procedure or to be specifically trained upfront any participation to the ECOLIFT study. Experience of at least 15 cases will be required. If the selected surgeon does not have sufficient experience, specific assistance will be provided by the company for his/her training (visit in an expert center for case observation, surgical mentoring for at least 5 cases, and 10 additional cases performed alone with possible critical review of a recorded video by an expert).

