3.2. SECONDARY OUTCOMES MEASURES

Secondary endpoints will be:

- The incremental cost/Qaly of PUL compared to transurethral surgery at 12 months
- The total hospital cost of each surgery procedure based on a top down micro-costing method performed during hospitalization stay
- Overall and specific urogenital healthcare consumptions at 4 months, 1 year and 3 years following the surgical procedure
 - Dispensed medications identified using the corresponding codes of the Anatomical Therapeutic Chemical (ATC) Classification;
 - o In- and out-patient visits;
 - Hospitalisation and their corresponding discharge diagnoses coded according to International Classification of Disease, 10th revision;
 - Medical procedures;
 - Nursing acts and physiotherapy;
 - Medical imageries and lab tests;
 - Transport;
 - Sick allowances;
 - At 4 months: all healthcare consumptions which are not reimbursed, but payed by the patient (e.g.: urinary incontinence products).

• BPH retreatment,

• Any dispensing of the following medications at 1 and 3 years after surgical procedure: alpha-blockers (ATC code G04CA) or 5-alpha-reductase inhibitors (ATC code G04CB);

 Hospitalization at 1 and 3 years after surgical procedure, with the main diagnosis of BPH (ICD-10 code N40) and the surgical procedure codes JGNE003, JGNE171, JGNJ001, JGFA005 JGFA009, JGFA015, JGFE023, JGFE365.

Urinary symptoms,

- Urinary incontinence evolution between inclusion and 4 months after surgical procedure (Incontinence Severity Index (ISI));
- International consultation on Incontinence questionnaire for Urinary incontinence short form (ICIQ-UI SF)
- Hospitalization with a discharge diagnosis ICD-10 code related to an urinary infection (code N41 for acute prostatitis or code N10 for acute pyelonephritis) at 1 and 3 years after surgical procedure;
- Hospitalization with a discharge diagnosis ICD-10 code related to urinary retention (R33) at 1 and 3 years after surgical procedure;
- Hospitalization with a discharge diagnosis ICD-10 code and/or medical procedure related to urethral stricture at 1 and 3 years after surgical procedure.

• Global quality of life,

- IPSS and IPSS-Q8 evolution between inclusion, 4 month, and 1 year after surgical procedure;
- O Jenkins sleep questionnaire between inclusion, 4 months, and 1 year after surgical procedure;
- EQ-5D-5L questionnaire (appendix 2) evolution between inclusion, 4 months, and 1 year after surgical procedure;

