7. STUDY INTERVENTION

7.1. INVESTIGATIONAL PROCEDURE: PROSTATIC URETHRAL LIFT

Prostatic urethral lift (PUL) consists in transurethral placement of permanent UroLift implants in both lateral lobes of the prostate. PUL intends to retract the lateral lobes of the prostate in order to reduce prostatic obstruction.

Based on clinical studies, between four to six implants are needed to treat one patient (based on the results of the Lift study) but the number of implants needed to treat each patient will be left at the discretion of the surgeon inside clinical study.

All procedures will be performed under local anaesthesia. Nitrous oxide inhalation use will be permitted, but we won't use oral or intravenous sedation.

In order to avoid complications related with the learning curve a proper training of the surgeons will be organized upfront starting of clinical study: a minimum of 15 cases performed under local anaesthesia in a day-care surgical unit will be required before entering clinical study.

One surgeon per investigating center will be trained and qualified to include patients in the PUL group.

Cases with obstructive median lobe of the prostate will not be excluded as was done in the precedent PUL studies (LIFT and BPH6), but will be treated only by advanced users as in the recently published MedLift study.

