10. MANAGEMENT OF ADVERSE EVENTS AND NEW DEVELOPMENTS

10.1. DURING THE CLINICAL TRIAL

Adverse events / undesirable effects / incidents will be declared to the various circuits of health vigilance applicable to each product or practice concerned (care vigilance, pharmacovigilance, materiovigilance, haemovigilance, cosmetovigilance ...) in accordance with the regulations in force.

Registrants should specify that the participant is included in a clinical trial and accurately identify the clinical trial concerned.

If the investigator becomes aware of a breach of patient safety in the course of the research, he must inform the sponsor without delay.

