11.2.4. SECONDARY CRITERIA

The following analyses will be performed for each cohort, according to the matched treatment group:

- An estimation of the total hospital cost of each surgery procedure based on a top down micro-costing method performed during hospitalization stay;
- A description of the overall and specific urogenital healthcare consumptions during the 3 years of follow-up;
- A description of BPH re-treatment over the 3 years of follow-up (number of patients with a new BPH medication, number of patients hospitalized for BPH surgical procedure);
- A description of urinary symptoms (value of the IPSS, ISI, ICIQ-UI SF scores during the 1st year of follow-up and number of patients with hospitalization for urinary infection, for urinary retention, or for urethral stricture during the 3 years of follow-up);
- A description of the quality of life during the 1st year of follow-up using the IPSS-Q8 score, the Jenkins sleep questionnaire, the EQ-5D-5L questionnaire;
- A description of the recovery after surgery using the Quality of Recovery visual analogue score and the time before returning to normal professional activities;
- A description of the sexual side effects during the 1st year of follow-up using the IIEF15 and MSHQ-EjD questionnaire;
- A description of the associated complications (number and types).

[figure not shown]
A detailed analysis plan will be defined and will be validated by the steering committee of the study. Subsequent modifications must be made before the blinding is lifted on the database and will be systematically validated by the Scientific Council.

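### The coded 1- and 3-year events miss late reoperations and stays in every cohort: no implant event, no bladder neck sclerosis or incontinence-surgery event, and surgical retreatment only under main diagnosis N40

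*Protocol*

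**What the plan says.** Section 3.2 lists the claims events to be read at 1 and 3 years:

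- Urinary infection: a stay with "code N41 for acute prostatitis or code N10 for acute pyelonephritis".
- Retention: "Hospitalization with a discharge diagnosis ICD-10 code related to urinary retention (R33) at 1 and 3 years after surgical procedure".
- Stricture: "Hospitalization with a discharge diagnosis ICD-10 code and/or medical procedure related to urethral stricture at 1 and 3 years after surgical procedure".
- Retreatment: a dispensing from either of two BPH drug classes, or a stay "with the main diagnosis of BPH (ICD-10 code N40) and the surgical procedure codes JGNE003, JGNE171, JGNJ001, JGFA005 JGFA009, JGFA015, JGFE023, JGFE365". Diagnosis and procedure are joined, so both are needed.

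Section 11.2.4 repeats the three urinary events for analysis: "number of patients with hospitalization for urinary infection, for urinary retention, or for urethral stricture during the 3 years of follow-up". Section 11.2.1 plans Kaplan-Meier estimates and logrank tests for retreatment and urinary symptoms. The Clavien-Dindo complication endpoint in 3.2 is fixed at 4 months.

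Section 7.1 describes PUL as "transurethral placement of permanent UroLift implants in both lateral lobes of the prostate". Section 1.1.2.1 names three delayed complications of transurethral surgery that may need further operations: urethral stricture, bladder neck sclerosis and urinary incontinence.

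**The concern.** The late comparison is one of the stated reasons for the claims phase: section 1.3 says that some consequences of surgery appear after 4 months and after 1 year. An event list for that purpose should catch the late consequences the protocol itself expects, in every cohort, by the same rule.

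The list falls short in three ways. It has no event for an implant, although only PUL leaves one. It has an event for one of the three late harms of transurethral surgery that the protocol names, and none for the other two. It also makes surgical retreatment depend on the main diagnosis, so a reoperation with a listed procedure code but a main diagnosis other than N40 is not a retreatment.

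At stake are the secondary comparisons of retreatment and late urinary events, which will go into a reimbursement file. The primary endpoint at 4 months is not affected.

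**Working it through.** **1. Where each late event after month 4 would be counted**

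| Event | Urinary events (3.2, 11.2.4) | Surgical retreatment (3.2) | Clavien-Dindo endpoint | Elsewhere |
|---|---|---|---|---|
| Urethral stricture | Yes | Only with N40 and a listed code | No (month 4) | Consumption; Visit 5 |
| Reoperation with a listed code, main diagnosis not N40 | Only if it also meets a urinary-event definition | No | No | Consumption; Visit 5 |
| Implant removal or revision | Only if it also meets a urinary-event definition | Only with N40 and a listed code | No | Consumption; Visit 5 |
| Device-complication stay | Same | Same | No | Consumption; Visit 5 |
| Bladder neck sclerosis surgery | Same | Same | No | Consumption; Visit 5 |
| Incontinence surgery | Same | Same | No | Consumption; Visit 5 |

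Visit 5 is at month 12 and exists only for the PUL and TURP/laser cohorts. For the SNDS cohort, and for everyone in years 2 and 3, claims are the only source.

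Two limits apply. Section 5.2.1 explains three of the eight procedure codes (TURP, HLE, GLV); the other five are unexplained, so the protocol alone cannot show that none relates to PUL. Section 6 says associated diagnoses are generally not used to define an outcome, so a device stay with retention or infection only as an associated diagnosis may also be missed.

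**2. Direction of the error**

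Let *q* be the share of PUL men, and *r* the share of comparator men, whose only late event is an uncovered one. For a measure of any late event:

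observed difference (PUL minus comparator) = true difference − *q* + *r*

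Neither *q* nor *r* is in the protocol. With assumed values, *q* = 5% and *r* = 1% shift the difference by 4 points in favour of PUL; *q* = 1% and *r* = 5% shift it by 4 points against PUL; *q* = *r* leaves it unchanged.

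**3. Precision available**

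Section 11.1 gives half-widths of 7% to 11% for 80 patients and 3% to 5% for 400. With 1.96 × √(p(1−p)/n) at p = 10% and 50%, I get 6.57% and 10.96% for n = 80, and 2.94% and 4.90% for n = 400. The stated figures reproduce.

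**4. Illustration for the implant component alone**

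Assumptions, none from the protocol: an implant-only event rate *q* over 3 years; a true any-late-event rate of 15% in both groups; *r* = 0. The last makes this the extreme one-sided case. Expected PUL men are 80 × *q*; the chance of at least one is 1 − (1 − *q*)^80; the half-width of the difference is 1.96 × √(p₁(1−p₁)/80 + p₂(1−p₂)/n₂), with p₁ = 15% − *q* and p₂ = 15%. The last column is the normal-approximation chance of a significant result in favour of PUL when there is no true difference (2.5% when *q* = 0).

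| *q* | PUL men of 80 | At least one | Half-width 80 v 80 | Half-width 80 v 400 | False PUL advantage, 80 v 400 |
|---|---|---|---|---|---|
| 1% | 0.8 | 55% | 10.9 points | 8.4 points | 4% |
| 2% | 1.6 | 80% | 10.7 points | 8.2 points | 6% |
| 5% | 4 | 98% | 10.2 points | 7.4 points | 19% |
| 10% | 8 | >99% | 9.2 points | 5.9 points | 73% |

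At 1% to 2% the effect on inference is small. It becomes material only at several percent, and any *r* above zero offsets it.

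**The case against.** A reader might infer that late harm is under-counted for PUL only, that PUL-specific harm is zero by definition after month 4, that no such stay would be reported, and that the bias favours the device. The protocol does not support this.

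- Bladder neck sclerosis and incontinence surgery, both late consequences of transurethral surgery according to section 1.1.2.1, have no claims event either. The list is incomplete on both sides, so the net direction is open.
- Overall healthcare consumption at 1 and 3 years covers stays with their discharge diagnoses and medical procedures. A reimbursed implant stay enters it.
- Visit 5 records any Clavien-Dindo complication at month 12 in both clinical cohorts, with no exclusion for device events. Incontinence symptoms are also measured there by questionnaire.
- An implant problem that meets the retention, infection or stricture definition, or is treated by a listed procedure under N40, is counted.
- The urinary events are separate items, not a composite of late harm. A missing implant item does not distort the stricture or retention result.
- Section 1.6 reports that the health authority wanted data on "the mid-long term functional results, and the need for any kind of retreatment", but it asked this of the company and did not set this study's endpoints. The device route in 10.1, within "pharmacovigilance, materiovigilance, haemovigilance", is a general reporting list.
- Outcome coding is deferred to a data management plan and an SAP not shown.

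All but the last stand and limit the claim. The deferral does not remove the point, because 3.2 already fixes the diagnoses, the procedure codes and the N40 condition. A later document can code these events but would have to depart from 3.2 to widen them. Consumption measures resource use; it does not put a late reoperation into the retreatment or urinary-event analysis. Visit 5 says nothing about years 2 and 3 or the SNDS cohort.

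**Conclusion.** The point holds in limited form. The coded late events are incomplete for all cohorts. A reoperation under a main diagnosis other than N40, an implant removal, a device-complication stay, or surgery for bladder neck sclerosis or incontinence after month 4 is left out of the retreatment and urinary-event comparisons unless it also meets a listed code. These stays are not lost from the study, but they are not compared as events.

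The event rate and the net direction of bias cannot be determined from the protocol. The only sizes available rest on assumed rates: 0.8 to 4 PUL men of 80 at 1% to 5%. The possible effect on significance is small at 1% to 2%, and about 19% against a nominal 2.5% at 5% in the one-sided case with a 15% base rate. This concerns secondary outcomes and merits correction because the remedy is cheap.

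**What to change.** In 3.2 and 11.2.4, add one event at 1 and 3 years, defined identically in all cohorts: any stay or procedure on the prostate, urethra or bladder after the index stay, whatever the main diagnosis. Report as named components:

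- implant removal or revision, and device-complication stays;
- surgery for bladder neck sclerosis;
- incontinence surgery.

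Compare PUL with both the TURP/laser and SNDS cohorts, alongside the existing list, which stays as it is. Also state what the five unexplained retreatment codes stand for.

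The cost is a code list in the SAP and the Data Extraction Plan. Section 14.3 already provides for extracting hospital summaries and outpatient claims, so no patient contact or new data source is needed. The downside is that the broader event will include some procedures unrelated to the BPH surgery; the named components and the retained narrow definitions let a reader see how much that matters.

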4. STUDY DESIGN AND METHODOLOGY OF ECONOMIC EVALUATION

4.1. STUDY DESIGN

ECOLIFT is a multicenter cohort study conducted on 3 cohorts as follows:

- The PUL cohort: a sample of surgeons from the 7 investigational centers will prospectively include 80 patients with a PUL surgery in first line treatment for BOO with a 1-year follow-up. Clinical data will be enhanced with healthcare consumptions and hospitalizations from SNDS with 2-year history before BPH surgery and a follow-up of 3 years.
- The TURP/laser cohort: a sample of surgeons from the 7 investigational centers different from those who will perform the PUL procedure (if not possible, it can be exceptionally the same surgeon) will prospectively include 80 patients with a TURP or laser (HLE or GLV) surgery in first line treatment for BOO with a 1-year follow-up. Clinical data will be enhanced with healthcare consumptions and hospitalizations from SNDS with 2-year history before BPH surgery and a follow-up of 3 years.
- The SNDS cohort: will include patients from the SNDS with any transurethral surgery (TURP, HLE or GLV) in first line treatment for BOO randomly matched to patients of the PUL cohort; For each transurethral surgery (TURP, HLE or GLV), 5 patients will be matched to 1 PUL patient using a high dimensional disease risk score (hDRS) based on the one-year SNDS information before transurethral procedure. The Disease Risk Score (DRS) estimates the probability of complications occurrence in the absence of the surgery of interest (PUL). DRS will be computed from a multivariable logistic regression model using a large set of variables collected during the one-year period among the SNDS cohort.

4.2. METHODOLOGY OF ECONOMIC EVALUATION

The economic evaluation will be conducted from the French Healthcare System point of view. This means that all healthcare expenditures and costs assumed by the French Healthcare Insurance, hospitals and patients will be taken into account in the analysis.

The incremental cost/avoided complication at 4 months between the PUL and TURP/laser cohorts, will be based on the following criteria:

• Differences in costs between both strategies:

- A micro-costing measurement will be performed in both groups during hospital stay to provide the total cost of each procedure. To identify costs, we will directly observe the resources used during the hospital stay that are related to each surgical procedure including human resources, materials, consumables and equipment.... Because it will not be possible to perform micro-costing for all items over the whole hospital stay, we will also use gross-cost hospital databases for some items (laundry, bedrooms, catering, general daily care, hospital equipment). Although it would be relevant to carry out a multicentric analysis on all recruiting centers, we prefer to restrict this analysis to the patients participating in the study in 3 hospitals: Bordeaux, Lyon and Lille University Hospitals and one clinic, the clinic la Croix du Sud at Quint Fonsegrives. This is justified because this kind of surgery seems to be standardized and doesn't vary a lot from one surgeon to another. Furthermore it will be easier to organise data collection in these centers, which are very used to economic studies. We intend to collect data for 5 patients/surgeries in each group, which means a total of 30 patients/surgeries included in the costing study. This choice could induce a lack of representativeness that we will study carefully by 2 ways before drawing our conclusions in the final report: 1- during collection data: we will study the variability of surgical practices through the filling of micro-costing questionnaires. If, at the end of the 30 observations, the questionnaires are very heterogeneous, we will continue to collect data in order to ensure representativeness of our costing study 2during statistical analysis, we will perform sensitivity analyses on cost data.
- Ouring the first 4 months after hospital discharge all expenses related to healthcare consumptions, reimbursed and not reimbursed, will be systematically collected at each follow-up visits by the participant of the study. Follow-up visits will be scheduled every month (including phone call with clinical research assistant and medical appointments).

• Differences in complications:

Complications will be classified according to the Clavien Dindo classification of adverse events.

The incremental cost/Qaly at 1 year between the PUL and TURP/laser cohorts will be based on the following criteria:

Differences in costs between both strategies:

- The total cost of hospitalization assessed by the micro-costing method described before.
- During the 12 months after hospital discharge all reimbursed expenses related to healthcare consumptions of each participant in each cohort will be gathered using SNDS claims databases.

• Differences in Qaly:

• The EQ-5D-5L questionnaire (appendix 2) will be fulfilled by the participants at the inclusion, at 4 months and at 1 year after initial surgery.

Statistical methods associated with this economic evaluation are described in chapter 11.

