1.3. JUSTIFICATION OF THE METHODOLOGICAL CHOICES

A two-phases economic evaluation

Randomized controlled trials were yet conducted and the remaining question is the cost effectiveness of PUL compared to other transurethral procedure in French daily practice. That's the reason why, we decided to propose an economic evaluation as the primary objective of this study.

In order to provide all pertinent clinical and economical information comparing PUL and TURP/laser surgery over a long-term follow-up period in the French context, we propose to conduct a study in two phases.

1-In the first phase we will prospectively compare a cohort of patients treated with PUL to another cohort of patients treated with TURP/laser during one year follow-up. This part of the study will enable us to gather real-life unknown information on the use of Urolift in French hospitals daily practice and organisation (number of implants needed, length and cost of surgery, length of hospital stay...) and to collect quality of life and clinical data from French population.

2- As some consequences of the surgery, as well as differences between healthcare consumptions, can occur even after 4 months and 1 year, and because it is difficult to pursue the clinical trial over 1 year without too many lost for follow-up patients, we decided to work on health databases for the second part of this study. This second phase will cover a 3-years follow-up by analysing healthcare resources utilization in each cohort using the French nationwide claims database, the SNDS. The comparison between PUL and TURP/Laser procedures will be strengthened by a complementary analysis performed between the PUL cohort and a matched cohort of patients identified in the SNDS database with the same baseline characteristics but treated with transurethral procedures. The matching process (based on a hdDRS) and the statistical methods of adjustment will overcome the absence of randomization in the initial process of patients' assignment to the PUL or TURP cohort.

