11. STATISTICAL ASPECTS

11.1. CALCULATION OF STUDY SIZE

In the SNDS, the study size will depend on the number of patients initially recruited. The expected number of patients will thus be for:

- **PUL Cohort:** 80 patients with PUL;
- TURP/Laser Cohort: 80 patients for the TURP or laser surgery
- **SNDS Cohort:** 1200 patients distributed between 400 matched TURP patients, 400 matched HLE patients and 400 matched HLV patients.

80 patients (in each of the PUL and TURP cohorts) will allow 95% confidence intervals with a precision:

- between 7% and 11% for observed proportions between 10% and 50%
- between 13% and 26% for observed means with coefficient of variation between 0.6 and 1.2.

Furthermore, 80 patients in each PUL and TURP cohorts is largely enough to answer to the primary economic objective (cost-effectiveness ratio, expressed as incremental cost/avoided complications) with a power of 80% and an alpha risk of 5%. In fact, according to the Glick formula¹, the needed number to treat to answer this question is about 40.

400 patients in each of the 3 subgroups of the SNDS cohort will allow 95% confidence intervals with a precision:

- between 3% and 5% for observed proportions between 10% and 50%,
- between 6% and 12% for observed means with coefficient of variation between 0,6 and 1,2.

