11.2.3. COST-EFFECTIVENESS CRITERIA

We will assess the cost-effectiveness ratio as following: $\Delta C/\Delta E = (Ceval - Cref)/(Eeval-Eref)$ where

- $\Delta C = \cos t$ differences between both surgery
- ΔE = effectiveness differences between both surgery
- Ceval = Cost of PUL surgery
- Cref = Cost of classical surgery (TURP/laser)
- Eeval = Complications observed at 4 months in the PUL group
- Eref = Complications observed at 4 months in the TURP/laser group

The ratio assessment for the second economic criteria (incremental cost/Qalys at 12 months) is the same.

First an unadjusted estimate of the cost-effectiveness ratios will be made. Their 95% confidence interval of the ratio will be estimated by bootstrap. We will then estimate the net monetary benefit of each surgical procedure (BNM = E λ - C), where λ is the differential cost - effectiveness threshold. The distribution of each BNM will be determined by boostrap. This will allow us to develop an acceptability frontier, a curve representing the probability that the BNM of each surgical treatment will be highest for each value of λ between $0 \in$ and $30000 \in$ per avoided complication (or Qaly in the secondary criteria).

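### The micro-costing total of 30 does not fit four sites, and the 80-per-arm precision and power do not describe the micro-costed hospital cost, which is directly observed in about 15 to 20 stays per arm

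*Protocol*

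**What the plan says.** Protocol section 4.2 describes the hospital part of the cost difference: "A micro-costing measurement will be performed in both groups during hospital stay to provide the total cost of each procedure". The work is limited to "3 hospitals: Bordeaux, Lyon and Lille University Hospitals and one clinic, the clinic la Croix du Sud at Quint Fonsegrives". The planned number is: "We intend to collect data for 5 patients/surgeries in each group, which means a total of 30 patients/surgeries included in the costing study". Some items (such as rooms, catering and general daily care) come from hospital gross-cost databases. The rule for going further is: "If, at the end of the 30 observations, the questionnaires are very heterogeneous, we will continue to collect data". Sensitivity analyses on cost data are also promised. Both measures are offered as answers to a possible lack of representativeness.

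The same section uses this hospital cost in the 4-month cost per avoided complication and again in the 12-month cost per QALY. Follow-up costs, by contrast, are gathered for every participant.

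Section 11.1 states that 80 patients in each cohort give a 95% precision "between 13% and 26% for observed means with coefficient of variation between 0.6 and 1.2", and that 80 per cohort is ample for the primary economic objective with 80% power at a 5% alpha. It does not mention the costing subsample. Section 11.2.3 says the "95% confidence interval of the ratio will be estimated by bootstrap". It does not say what is resampled or how patients outside the subsample receive a hospital cost.

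Section 1.3 says the first phase will gather, from routine practice, items such as "number of implants needed, length and cost of surgery, length of hospital stay".

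**The concern.** There are two linked problems.

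The first is a contradiction within one paragraph. Two groups, five surgeries in each and four named sites do not give 30. The figure is both the planned size of the costing study and the point at which the team decides whether to collect more, so it is not a harmless slip.

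The second is that the precision and power in 11.1 rest on 80 per arm, while one component of the primary ratio's numerator is directly observed in a fraction of that. Section 1.1.2.3 puts implants at about €500 each with a mean of four, and mean hospital income per stay at about €2253, so the index stay is unlikely to be a small part of the cost. The study hypothesis is that implant cost is offset by savings elsewhere. A reader of 11.1 would credit the cost difference with more precision than the design delivers. Depending on how un-costed patients are handled, the interval of the ratio and the net monetary benefit curve could inherit that error.

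**Working it through.** **Count.** Inputs from section 4.2: 5 surgeries per group, 2 groups, 4 sites.
- With no site factor: 5 × 2 = 10.
- Three sites: 5 × 2 × 3 = 30.
- Four sites: 5 × 2 × 4 = 40.

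So 30 implies a multiplier of three. Spread over four sites it would be 7.5 per site. Split equally between arms (an assumption), 30 means 15 per arm and 40 means 20 per arm. The stays without micro-costing number 160 − 30 = 130, or 160 − 40 = 120.

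**The plan's own precision.** Relative 95% half-width of a mean = 1.96 × CV / √n. At n = 80:
- CV 0.6: 1.96 × 0.6 / √80 = 13.1%
- CV 1.2: 1.96 × 1.2 / √80 = 26.3%

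This reproduces the 13% and 26% of section 11.1. The figures are correct for a mean observed in 80 patients.

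**The same formula at the costing numbers.**

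| CV | n = 15 | n = 20 | n = 80 |
|---|---|---|---|
| 0.2 (assumed) | 10.1% | 8.8% | 4.4% |
| 0.3 (assumed) | 15.2% | 13.1% | 6.6% |
| 0.6 | 30.4% | 26.3% | 13.1% |
| 1.2 | 60.7% | 52.6% | 26.3% |

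Whatever the CV, the half-width is √(80/15) = 2.31 times that at 80 per arm, or √(80/20) = 2.0 times. With the t quantile in place of 1.96, the n = 15 figures at CV 0.6 and 1.2 become 33.2% and 66.5%.

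**What this could do to the bootstrap interval.** The protocol gives no variances, so this is an illustration under assumptions: hospital cost mean €2250, follow-up cost mean €500 with CV 1.2, the two independent, no true difference between arms, 15 costed stays per arm, and the subsample mean assigned to all 80.

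Variance of the cost difference from follow-up cost: (500 × 1.2)² × 2/80 = 9000.
Variance from the costed stays at CV 0.2: (2250 × 0.2)² × 2/15 = 27000. The total is 36000.

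A bootstrap over the 80 patients alone sees only the 9000. Its standard error is √(9000/36000) = 0.5 of the true one, so a nominal 95% interval covers with probability P(|Z| < 1.96 × 0.5) = 67%. At CV 0.6 the costed stays contribute (2250 × 0.6)² × 2/15 = 243000, the fraction is √(9000/252000) = 0.19, and coverage is about 29%.

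A simulation with lognormal costs agrees. Half-widths are for the cost difference.

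| Hospital-cost CV | Coverage, patients only | Coverage, costed stays also resampled | Half-width, patients only | Half-width, both | Half-width if all 80 were costed |
|---|---|---|---|---|---|
| 0.2 | 65% | 93% | €175 | €352 | €222 |
| 0.3 | 49% | 92% | €177 | €487 | €273 |
| 0.6 | 29% | 92% | €174 | €903 | €445 |
| 1.2 | 15% | 90% | €176 | €1673 | €813 |

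With all 80 costed, coverage in the same simulation was 92% to 94%, so resampling both levels comes close to what complete data would give.

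**The case against.** The strongest reply is that the protocol never says a subsample mean will be assigned to all 80. Section 1.3 foresees collecting implant numbers, length of surgery and length of stay, and the assessment table in 9.2 lists hospitalization cost at the intervention without restricting it to some sites. Patient-level costing may be what is intended, and the detail can properly sit in an SAP that is not at hand. This stands. A reader might infer that the interval is simply far too narrow; the documents support that only under the conditions stated above.

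Other points also stand in part:
- Thirty is a starting number, some items come from gross-cost data, and sensitivity analyses are planned. But the extension rule has no threshold, and it and the sensitivity analyses address representativeness, not precision.
- Section 4.2 never writes that the five are per site. No other multiplier is given, however, and without one the total would be 10.
- Section 11.1 speaks of means in general, not of hospital cost, and section 4.2 regards the surgery as standardized. A CV of 0.6 to 1.2 may therefore be too high for the index stay, which is why 0.2 is shown alongside. The ratio to the 80-per-arm precision does not depend on the CV.

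Three further readings are tempting but unsupported. One is that 15 per arm falls below the requirement of about 40 in section 11.1. That figure concerns the cost-effectiveness question as a whole, its inputs are not given, and it is not said whether it is per arm or in total. Another is that a bootstrap cannot be used. Section 11.2.1 names it for costs with counts under 100, so it can be applied to a small costing sample. The last is that the hospital stay is the main cost item. That is a fair inference from the implant and income figures, but follow-up costs are not given.

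**Conclusion.** The point holds in two parts. First, the total of 30 and the extension trigger do not agree with four named sites: on the only multiplication that yields 30, four sites give 40. Second, the precision and power in section 11.1 are silent on a component of both ratios that is directly observed in about 15 to 20 stays per arm at the start. For that component, precision is 2.0 to 2.3 times worse than at 80 per arm: 30% to 61% (15 per arm) or 26% to 53% (20 per arm) at the CVs of 11.1, and about 10% against 4.4% for 15 per arm if the CV is 0.2. These figures assume an equal split between arms and no extension of the sample.

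Whether the interval in 11.2.3 is too narrow depends on a rule the protocol does not give. It is too narrow if subsample costs are carried to un-costed patients and only the patients are resampled. The coverage figures show that this would matter even at a low CV, but they rest on assumed means and variances.

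**What to change.** 1. In section 4.2, reconcile the total and the trigger with the four sites (40 if five per group per site is meant, or name the three sites), and state the number per arm and per site.
2. In section 11.1, say that the 80-per-arm precision and power do not cover the micro-costed component, and give its precision at the true number.
3. Cost each patient from his own resource use (implants, theatre time, length of stay) multiplied by unit costs from the costed stays, where these data are collected. Check that the e-CRF captures them at all seven centres.
4. In section 11.2.3 or the SAP, resample the costed stays together with the patients in every bootstrap replicate, so that their uncertainty reaches the ICER and the net monetary benefit.

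The cost is wording, possibly a few e-CRF fields and a nested bootstrap. The reported interval will be wider. In the illustration at CV 0.2 the half-width goes from €175 to €352 when costed stays are resampled as well, and by more at higher CVs. Step 3 should limit the widening, because variation between patients in resource use would then be observed in all 160.
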